#### Titration Schedule:

Adverse events: Study physician will review with study participants regarding the nature,

duration and severity of noted adverse events. The study physician will make clinical judgements on the relationship between reported adverse events with study medication. If there is a high likelihood of adverse events being related drug effects, the subject will titrate down from 16 IU/day (4 sprays per day) to 12 IU/day (3 sprays per day) and will be reassessed in one week). At the next assessment the side effects and tolerability will again be reviewed by the PI and medical monitor. If the side effects have resolved, the subject will be titrated back up to 16 IU/day. If the side effects persist, the subject may continue on the 12 IU/day for another week; or will be discontinued from the study at the judgement of the PI. Subjects who do not receive the full dose by week four will be discontinued. Any subject who is discontinued from the study will be referred for continued medical follow up.

Lack of response: One upward titration will be allowed at week 2 to 24 IU/day (4 sprays per day) if study clinician, with consultation of the PI, determines that study subject experiences no response on hyperphagia via a categorical yes/no determination, and has no adverse events. In our current ongoing pilot study, and in [name]'s study, the initial hyperphagia response was observed at the week 1 and week 2 ratings.

**Instructions for Dosing:** Once the cap has been removed from the spray, the device should be held upright to the nostril and the actuator depressed. The patient should be in the sitting position and should be instructed to inhale gently through the nose while the actuator is being depressed. The head should be tilted back once the actuator is depressed to ensure that no fluid runs out of the nose. Parents may assist the child with dosing.

**Outcome Measures:** Project outcomes will be determined by changes in scores of parent and clinician rated measures from baseline to week 8 and comparisons of week 8 measures between active treatment and placebo groups. Assessments will be administered according to the schedule of events in **Table 2**.

Safety monitoring will be completed at each visit in both remote and in-clinic settings. Participant will complete concomitant medication review, adverse event (AE) monitoring, ABC rating, and be monitored for hypogonadism, sleep apnea and lethargy, In addition, a complete physical and neurological exam and full panels of clinical labs (CBC, BMP, LFT, IGF-1, thyroid panel, lipid panel, HbA1C, testosterone, estrogen, growth hormone, ghrelin, pancreatic polypeptide, peptide YY, leptin, GLP-1, insulin and glucagon) will be completed at baseline and week 8 in person visits.

For participants who are able to provide salivary samples and co-operate with the collection process, the study team will attempt to obtain pre- and 1 hour post- study IP administration saliva at baseline, week4, and week 8 using the Oragene-Discover collection kit (ORG-500). The salivary samples will be used to measure patient oxytocin levels.

As required by the Division of Psychiatry Products and suggested by FDA review, we have also included the ABC-I subscale at every visit as a prospective assessment for suicidal ideation. The ABC will also be used to assess for adverse events, including increased aggression or temper tantrums. Urine pregnancy tests will be completed at every visit to ensure subject safety. If a subject becomes pregnant during the study, she will immediately be discontinued from the medication. All subjects must use abstinence or a valid method of non-estrogen based double barrier contraception to participate in the study.

While some of these secondary measures have not been studied in PWS, we believe that they

are appropriate for this population as a valid measure of treatment efficacy and focus on important target issues of PWS – including repetitive behaviors (Repetitive Behavior Scale-Revised). The WHOQOL is a validated measure used to assess quality of life and has been used in a vast array of clinical trials in varied disorders (muscular dystrophy, hypertension, tuberculosis, etc.). The Caregiver Strain questionnaire (CSQ) is a commonly used and well-validated self-report questionnaire developed to assess caregiver strain for families with a child living with an emotional or behavioral disorder. The ABC has been used to assess disruptive behaviors in other disorders such as Down Syndrome and other intellectual disabilities

**Study Time Commitment and Reduction of Burden:** Every effort to reduce the time burden on patients and caregivers has been made. In the era of COVID-19 pandemic and travel restriction, we are implementing telemedicine for remote visits in some of the study visits to reduce patient's potential exposure and travel, while ensure adequate study monitoring are in place.

The HQ-CT, ABC, WHOQOL, CSQ, MERS-PWS and RBS-R assessments are completed with the parent and not the patient, as specified in the schedule of events. As is the case in most clinical trials, the most significant burden to the parent and child is the screening visit, which is done remotely and avoided participant's need to travel. Each parent questionnaire takes between 5 and 25 minutes to complete and child assessments are kept to a minimum, with optional breaks to maximize patient comfort. Screening lab work will be done locally at participants nearest Quest lab. This is particularly beneficial for out of state participants. Clinical lab works are collected only at in person visits at baseline and week 8 during in person clinic visits. We have eliminated the eye- tracking measures as they are not central to our hyperphagia and repetitive behavior aims and to reduce burden. This ensures minimal burden to the family and decreases the time commitment while reducing testing bias on measures. As parent rated measures are questionnaires, no repeat testing bias is expected.

The time commitment and study burden is similar to other current studies in this population and the ASD population. If needed, visits can be split into two visits. Parents may prefer to attend a visit by themselves without the child to complete their measures. Visits at screening, weeks 2, 4, 6, and 10 (follow-up) are remote visits done via tele-medicine. The study clinicians will complete the video conference call with the parent. This will further reduce the family's burden and decrease the amount of times they need to travel to the study site. As much flexibility in scheduling as necessary will be given to the patients and families. Reimbursement for time and travel is provided at each visit (\$150 – in-person; \$30 – phone visit). Additional reimbursement for travel will be provided as needed for families traveling long distances. The average time needed for parents, child and clinician to complete the assessments is detailed below. Details about which measures are included in each visit can be seen in **Table 2: Schedule of Events.** Some assessments require the participation of both the parent and child and times reflect how long each individual is needed independent of combined measures. Families may differ in how long it takes them to complete certain measures and the times do not include any breaks for meals or walking between sites at the clinic.

Screening Visit (remote): 3-4 hours Baseline Visit (in-person): 4-5 hours Week 2 and Week 6 (remote): 30 minutes Week 4 (remote): 2-3 hours Week 8 (in-person): 4-5 hours Week 10 Follow Up (remote): 2-3 hours

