**Titration Plan and Schedule:** If side effects occur, the medical monitor, PI and co-I's will determine if and when to titrate based on severity of the adverse event and relation to the study drug. If there is a significant exacerbation of known PWS co-morbidities, including Type 2 diabetes, sleep apnea or hypogonadism, or any other adverse event rated by the study physician as severe, a clinical determination will be made by the medical monitor, PI and co-I's, as to the patient's eligibility to continue in the study, or to follow the titration schedule, as described below. Both co-investigators, [name] and [name], have extensive expertise in co-morbidities associated with PWS, as does consultant [name].

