These 3 categories are based on the Site Investigator's clinical judgment, which in turn depends on consideration of various factors such as the subject's reports, the physician's observations and the physician's prior experience. The severity of the AE should be recorded in the source documentation. The evaluation of severity is distinguished from the evaluation of "seriousness." A severe event might not meet the criteria for seriousness and a serious event might be evaluated as mild.

**Safety Analyses:** Safety will be evaluated from concomitant medications, study drug exposure, treatment emergent adverse events, serious adverse events, death, suicidal ideation, physical examinations, clinical laboratory test results and vital signs. All summaries of adverse events and suicidal evaluation will be presented. Serious adverse events, deaths (if any), abnormal laboratory results and abnormal vital signs will be listed in patient listings. All AEs will be coded by the system organ class (SOC) and preferred term (PT) using the Medical Dictionary for Regulatory Activities (MedDRA).

Non-treatment emergent AEs are defined as

- AEs that started and resolved prior to the first study drug dosing
- AEs that started prior to the first study drug dosing, resolved after first study drug dosing and the grade remained the same or reduced.

Treatment emergent adverse events (TEAEs) are defined as all AEs that begin or worsen after the patient receives the first dose of the study drug until follow –up. All reported AEs (including non-treatment-emergent adverse events) will be listed. Overall summary of TEAEs, such as total number of reported TEAEs, total number of patients reporting at least one TEAE, severity of TEAEs, relation to study drug, serious AEs, any deaths, TEAEs leading to study drug discontinuation, will be summarized by treatment group. In addition, TEAEs will be tabulated by SOC and PT. A table will contain the number of TEAEs (frequency of occurrence, number and percentage of patients) by treatment group will be created.

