For summaries of TEAEs by maximum severity, body system, and preferred term, the rule will be as follows: if a patient experiences more than one episode of a particular coded adverse event, the patient will be counted only once by the maximum severity of these episodes (preferred term). Similarly, if a patient has more than one adverse event within a body system, the patient will be counted only once by the maximum severity among adverse events in that body system. For the purpose of summary of adverse events, missing severity events will be included in the Grade 3 (Severe) event category. Summary of TEAEs by SOC and PT will also be presented fort the following categories, when data are available.

- 1. Grade 3 TEAEs
- 2. Related and Grade 3 TEAEs
- 3. TEAES leading to study drug discontinuation
- 4. Serious events
- 5. Serious and related events
- 6. Events resulting in death

Additional Safety Monitoring and Adverse Event Reporting Adverse events that are serious and unexpected will be immediately reported to the IRB, and FDA. Non-serious unanticipated problems will be described in annual reports to the IRB and FDA. Additionally, a pediatrician not affiliated with this study will serve as a medical safety monitor for this study. The safety monitor will review subjects' laboratory values and adverse events on at least a monthly basis. This physician will be available to immediately address the clinical circumstances for any acute problem and will promptly notify appropriate regulatory bodies.

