**Risks:**\_Studies have shown risks of IN-OXT to be minimal with no difference in AE burden between IN-OXT and placebo [46]. The most common categories of side-effects seen include:

- increased calmness/euphoria or more energy
- light headedness
- drowsiness/fatigue
- headache
- nasal irritation
- dry mouth/throat

As noted above, one study of IN-OXT in PWS noted increased levels of aggression, via temper tantrums, at higher doses of IN-OXT. As very few studies have reported on the extended use of IN-OXT there may be other unknown side effects, although our 6-week studies showed no difference in AEs. Other risks relate to venipuncture procedures for blood sampling taken at key points in the study as a safety measure. Blood draws and anthropometric measures will be completed at the CTSA sponsored Clinical Research Center (CRC), which has trained nursing and lab staff. In addition, patients may feel uncomfortable answering some of the questions presented during the assessments and breaks will be provided if needed. There is a risk of loss of confidentiality, although every step is being taken to keep patient files and data secure. All data is locked in staff offices or on staff computers and only authorized personnel or organizations indicated in the consent (IRB; FDA etc.) will have access. Pediatric neurologist [name], PhD is the independent medical monitor and will review side effects after each study visit to ensure subject safety and to determine if a subject's participation should be terminated due to an AE.

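### Children removed under the week-four dose rule would have no week-8 HQ-CT, because no outcome follow-up after discontinuation is planned

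*Combined protocol and SAP*

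**What the plan says.** Under the adverse-event part of the Titration Schedule, the rule reads "Subjects who do not receive the full dose by week four will be discontinued". It does not say from what. The sentence before it says that a child whose side effects persist may stay on the reduced dose or "will be discontinued from the study at the judgement of the PI". The sentence after it says "Any subject who is discontinued from the study will be referred for continued medical follow up". The Titration Plan and Schedule speaks of a determination "as to the patient's eligibility to continue in the study, or to follow the titration schedule", and the Risks section has the medical monitor decide whether "participation should be terminated due to an AE". Assessment of Safety ends adverse-event collection at the last visit of a child who withdraws or is discontinued from the study.

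Two other places speak of stopping drug only. A participant who becomes pregnant is covered by "she will immediately be discontinued from the medication" (Outcome Measures), and the safety tables include "TEAEs leading to study drug discontinuation, will be summarized by treatment group".

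The Primary Outcome section schedules the HQ-CT at every visit. No section says that visits or ratings continue after discontinuation.

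On analysis, the Statistical Analyses section keeps each child in the assigned group whatever the compliance. The week-8 score and its change are compared by t-test or Wilcoxon test, alongside mixed models and a responder comparison. The Missing data paragraph bases the primary analysis on the data available at each time point. The Power Analysis claims 80% power at d = 0.8 with 25 per arm.

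**The concern.** Intent-to-treat here fixes the group in which a child is analysed. It cannot supply a score that nobody collected. If a child leaves the study around week 4, no week-8 HQ-CT exists and the available-data rule omits that child from the week-8 two-sample test. No one is reassigned, so this is a missing-outcome problem, and the protocol itself creates it.

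The missingness is not haphazard, because the rule is triggered by adverse events judged likely to be drug-related. Removal could therefore be more common on oxytocin, and removed children might have scored differently at week 8. Either would separate the effect that the week-8 test estimates from the effect in all randomized children. With 25 per arm, a few children are enough to matter.

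**Working it through.** **1. What happens to a removed child in each planned analysis**

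| Analysis | Week-8 score absent |
|---|---|
| Week-8 t-test or Wilcoxon test | Child omitted |
| ANCOVA on the week-8 level (used if change depends on baseline) | Child omitted |
| Mixed model | Scores up to removal are used; valid if data are missing at random. The stated terms are time, treatment and their interaction, and the plan does not say whether baseline is among the repeated measures |
| Responder proportion | Clinical dropouts coded as non-responders, so no score is needed; this does not help the continuous comparison |
| Multiple imputation | Only if missingness differs across observed covariates; gives a modelled value |
| Sensitivity analyses | Promised; they test assumptions and do not recover the score |

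**2. The plan's power figure**

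Inputs from the Power Analysis: d = 0.8, 25 per arm, two-sided 5%, two-sample t-test. The non-centrality is d × √(n₁n₂/(n₁+n₂)) = 0.8 × √12.5 = 2.828, with 48 df and critical value 2.011. Exact power is 79.1% (80.7% by normal approximation). The stated 80% reproduces within rounding, but only with all 50 children evaluable.

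**3. Power under loss**

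The documents give no loss rate. Losses of 1, 3 or 5 of 25 (4%, 12%, 20%) are my assumption.

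| Lost | Equal loss in each arm | Active arm only |
|---|---|---|
| 1 | 77.4% | 78.3% |
| 3 | 73.6% | 76.4% |
| 5 | 69.3% | 74.1% |

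Baseline adjustment could offset this. Using d/√(1−r²) and one fewer df, with an assumed baseline to week-8 correlation r of 0.3 or 0.5, power for equal losses is 81.1% or 87.9% (1 lost), 77.5% or 84.9% (3 lost), and 73.3% or 81.2% (5 lost).

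**4. Gap between the two effects**

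Suppose k of 25 active children stop.

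- No benefit (extreme case): the effect in all randomized children is 0.8 × (25−k)/25 = 0.77, 0.70 or 0.64 for k = 1, 3 or 5.
- Half benefit: (0.8 × (25−k) + 0.4 × k)/25 = 0.78, 0.75 or 0.72.

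The test that omits these children targets 0.80 throughout.

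**5. Power if they are kept, k = 3**

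Simulating the mixed active arm (200,000 trials) gives about 67% with no benefit and about 74% with half benefit. The test that omits them has 76.4%, but for a different effect.

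**The case against.** The strongest case on the other side has four parts.

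*The wording is clear enough.* Read in context, the rule means leaving the study. The drug-only wording concerns pregnancy and table labels, and a trial can tabulate drug discontinuation and also remove some children. This largely stands. A reader might infer a contradiction between the passages, but the documents do not support that. What remains is that the natural reading ends outcome collection, and that the term is used in two senses.

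*Few children may be affected.* The Missing data paragraph expects low loss, and Preliminary Study 4 reports no downward titration so far among 9 randomized, blinded pilot subjects. This also stands, though nine children are little evidence: at a true rate of 20%, none in nine would still occur with probability 0.8⁹ = 0.13.

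*The plan already handles missing data.* It names non-ignorable missingness, plans sensitivity analyses, and will compare lost with retained patients. These steps are real mitigations, but all depend on assumptions about scores that could have been collected.

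*The remedy may lower power.* It may, as step 5 shows. The omitted-child test keeps more power only by answering a different question.

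A reader might also infer that the week-8 test describes only children on full dose. It does not: the rule acts only by week four, so a child reduced later can remain, and non-compliant children stay in the analysis.

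**Conclusion.** The point holds as a gap in outcome collection. Followed as written, the week-four rule produces tolerability-linked missing week-8 scores, and the week-8 two-sample test would then not cover all randomized children, as the intent-to-treat approach intends. Bias is possible, not certain. The rule applies to both arms under blinding, and the documents do not allow the size or direction of any bias to be known. The gap of 0.70 against 0.80 SD rests on an assumed 3 of 25 active children with no benefit at all; with half benefit it is 0.75 against 0.80.

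Power is secondary. A reader might infer that the trial is underpowered because of this rule, but the 80% reproduces, the loss rates are assumed, and a modest baseline correlation could offset the smaller losses. What is missing is a statement that the figure assumes complete data in an unadjusted t-test.

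**What to change.** Leave the treatment rule unchanged and make these changes:

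1. State that stopping study drug does not end outcome collection for families who remain in consent. Keep collecting the caregiver-rated HQ-CT at scheduled visits through week 8. Weeks 4 and 6 are already remote; week 8 is an in-person visit, so allow remote completion there for these children.
2. Include those scores in the primary intent-to-treat analysis, and report by arm how many children stopped under this rule and when.
3. Align the use of *discontinued* across the Titration Plan, Titration Schedule, Outcome Measures, Assessment of Safety and Risks sections, saying each time whether drug or study is meant.
4. Note in the Power Analysis that 80% (79.1% by the exact t) assumes all 50 are evaluable in an unadjusted t-test, and give power under a stated loss allowance.

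The cost is a few sentences of protocol and analysis text and a 15-minute questionnaire at already scheduled time points for the families affected. The statistical price is the possible dilution shown in step 5. A week-8 score that was not collected cannot be recovered later, so the change has to be made prospectively.

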# SPECIFIC AIMS

#### OBJECTIVE

The primary objective of this Phase 2 trial is to compare the change from baseline to week 8 of the peptide intranasal oxytocin (IN-OXT) on changes in hyperphagia using the Hyperphagia Questionnaire-Clinical Trials (HQ-CT) in children and adolescents with PWS. We have obtained an IND for the use of IN-OXT for PWS (IND 121109) and have acquired both the IN-OXT and matching placebo (Manufactured by Novartis as Syntocinon - see letter and COA of Batch in appendix). We will also compare the effects of IN-OXT from baseline to week-8 on repetitive behaviors (RBS-R), weight, BMI and body composition, quality of life (WHOQOL, Caregiver Strain Questionnaire), salivary oxytocin concentration, and safety measures. Safety will be assessed with routine laboratory monitoring, physical exam, urine pregnancy test for menstruating females, and collection of vital signs. The Aberrant Behavior Checklist (ABC) will also be used as a safety measure for both suicidality (per FDA guidelines) and for adverse events (aggression/temper tantrums). This Phase 2 study is designed to generate preliminary data for future Phase 3 trials, and targets symptoms in this population that currently have no effective treatments. By treating these symptoms earlier in life in a pediatric PWS population we may maximize the treatment impact. This study supports the Orphan Product Divisions goal of identifying and promoting the development of treatments indicated for rare diseases or conditions. Our proposed treatment will target hyperphagia in subjects with PWS, a symptom for which there is currently no effective treatment.

This study will provide essential data that is needed for drug development and eventually drug approval.

We propose a three-year randomized, double-blind, placebo-controlled 8-week treatment trial of IN-OXT 16 IU/day in 50 subjects aged 5 to 17 years with PWS. To allow for dose optimization, we allow one downward titration to 12 IU if adverse events occur, and one upward titration to 24 IU at week 2 for lack of response on hyperphagia.

**Primary:** To compare IN-OXT vs. placebo on changes on the Hyperphagia Questionnaire-Clinical Trials (HQ-CT) from baseline to week 8 in children with PWS. We hypothesize that IN-OXT will be significantly superior to placebo in improving hyperphagia.

Secondary: To compare the change from baseline to week-8 of IN-OXT vs. placebo on:

- 1. Repetitive Behavior Scale-Revised (RBS-R).

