#### **Exploratory:**

- 1. To compare IN-OXT vs. placebo on changes in dietary intake using the ASA 24: Automated, Self- Administered, 24 hour Recall diet diary system, as provided by the National Cancer Institute (NCI).
- 2. To examine the impact of medical co-morbidities on treatment outcome.
- 3. To examine the relationship between weight-based dosing and treatment response on hyperphagia.

4. To compare IN-OXT vs. placebo on changes in hormone levels at baseline and endpoint. Measured hormones will include ghrelin, pancreatic polypeptide, peptide YY, GLP-1, insulin, glucagon, testosterone and estrogen. We will also look at changes in HbA1C.

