**Research Strategy And Feasibility:** We propose a three year, phase 2, randomized doubleblinded 8-week treatment trial of IN-OXT vs. placebo in 50 child and adolescent subjects (25 male and 25 female) aged 5 to 17 years with a diagnosis of PWS. PWS diagnosis will be confirmed by study team via patient interview and confirmation by patient's past medical records and genetic testing results. At the screening visit, patient will have the opportunity to learn about the study and seek clarification on any outstanding questions. If patient voluntarily agree to participate, study team will work with the patients to complete the informed consent and if applicable, assent. In addition, a psychiatric interview and medical history review will be conducted to screen the patient for eligibility. The study team will also review patient's concomitant medications, assess for patient condition with CGI-S and hyperphagia using the Hyperphagia Questionnaire-Clinical Trials (HQ-CT). If patient meets selection criteria, the study team will arrange on behalf of the patient for an out-patient Quest visit, at which time patient will be asked for a screening blood draw to provide information on CBC, BMP, LFT, IGF-1, thyroid panel, lipid panel, testosterone, estrogen, hemoglobin A1C, and for applicable patient, a urine pregnancy test. Once the screening blood work results are available and all results are within acceptable range, and patient is otherwise eligible, patient will be invited for an in person visit to clinic where additional assessments including a complete physical and neurological exam, intelligence test, interval health or medication change, and if applicable, repeat urine pregnancy test will be conducted. If patient continues to meet all study inclusion and exclusion criteria and agrees to continue with study participation, the study team will formally submit the patient for randomization. The randomization is done in a 1:1 placebo to oxytocin ratio and stratified for gender. The result is blinded to the study team and the process is performed by the study pharmacist at the Clinical Research Pharmacy using a computer generated randomization table. Patients will receive a supply of oxytocin spray bottle with each spray dispensing 4 IU, or a matching placebo. The participant will start with an initial dose of 2 sprays per nostril (4 sprays per day), or 16 IU/day IN-OXT or placebo. To allow for optimization for adverse events or lack of response, we allow for one downward titration to 12 IU (3 sprays per day), and one upward titration to 24 IU (6 sprays per day) at week 2. This will also allow us to examine the relationship between weight based dosing and treatment response. Syntocinon (synthetic intranasal oxytocin) and matched placebo made by Novartis will be used in this protocol. We have an IND for the use of IN-OXT in PWS (IND 121109).

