#### Adverse Event Reporting and Measures of Compliance:

Drug accountability will be completed by the Pharmacist at the Clinical Research Pharmacy and will serve as a measure of study compliance. IN-OXT and Placebo nasal spray bottles will be weighed pre-and post- dispensing to ensure the correct amount of drug/placebo was administered to the patient. The pharmacist will notify the study team if a subject is non-compliant with the study drug/placebo, and the study team will address this with the subject and his/her parent.

Adverse events will be reported on logs kept in the subject binder and completed by the study physician at each visit. Reporting requirements for the FDA (within 7 days) and the IRB (within 5 days) will be followed for any suspected unexpected related adverse event. For any SAE the IRB will be notified within 24 hours, and the FDA within 48 hours.

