#### Additional Analyses

 Sample size permitting, we will explore the potential for ethnicity-by-treatment interactions. If effects of minority status are found that might be clinically meaningful, even if not statistically significant, we will report these to guide future research. Please see the Planned Enrollment Table for the breakdown of anticipated percentages of children of each ethnicity that will be enrolled.

- 2. We will test for gender by treatment interactions.
- 3. We will explore IQ by treatment interactions.
- 4. We will explore for co-morbidity (e.g. Type 2 Diabetes, Hypogonadism etc.) by treatment interactions.
- 5. We will explore for weight based dosing by treatment interactions.

**Missing data:** In any clinical trial, some subjects will be lost to follow up or will miss study visits but the expected rate is low given that this is only an 8 week trial. Primary analysis will be based on available data at each time point. The advantage of the linear mixed effects approach is that it can handle data which are missing at random and measurement times which are not evenly spaced. However, when the missingness mechanism depends on unobserved information, i.e., non-ignorable, parameter estimates and resulting tests on hypotheses will be biased without further adjustment. Different approaches for handling missing data will be performed in this study. Multiple imputation will be applied if missing data rates are observed to differ across observed covariates. Regardless of the technique, characteristics of patients who are lost to follow-up will be compared to those that remain in the study to assess the degree of any selection bias, and sensitivity analyses will be performed to evaluate robustness of conclusions to the different missing data approaches.

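### The Titration Schedule gives the week-2 escalated dose of 24 IU/day as 4 sprays; at 4 IU per spray that is the unchanged 16 IU starting dose, and the count should be 6.

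*Combined protocol and SAP*

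**What the plan says.** The up-titration is described in two places that give a spray count, and they disagree.

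- **Titration Schedule, lack of response:** "One upward titration will be allowed at week 2 to 24 IU/day (4 sprays per day". The step is for a child judged to have no response on hyperphagia and no adverse events. The study clinician decides it in consultation with the PI.
- **Research Strategy And Feasibility (under Approach):** "one upward titration to 24 IU (6 sprays per day) at week 2".

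The Research Strategy paragraph also gives the product strength: "Patients will receive a supply of oxytocin spray bottle with each spray dispensing 4 IU". It sets the starting dose at 2 sprays per nostril, 4 sprays and 16 IU per day.

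The adverse-event paragraph of the Titration Schedule, just before the lack-of-response rule, says "the subject will titrate down from 16 IU/day (4 sprays per day) to 12 IU/day (3 sprays per day".

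The Objective gives the escalated dose without a spray count: "one upward titration to 24 IU at week 2 for lack of response on hyperphagia". Background and Significance gives the same 24 IU.

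Two later parts of the plan depend on the dose actually taken. Under Adverse Event Reporting and Measures of Compliance, nasal spray "bottles will be weighed pre-and post- dispensing to ensure the correct amount of drug/placebo was administered to the patient". The exploratory aims include "To examine the relationship between weight-based dosing and treatment response on hyperphagia", and Additional Analyses adds "We will explore for weight based dosing by treatment interactions".

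**The concern.** The printed rule contradicts itself. A child who starts on 4 sprays and is escalated to 4 sprays has not been escalated. Because the strength per spray is fixed, a family changes the dose only by changing the number of sprays. The spray count is therefore the working instruction, and it is wrong for the one dose above the starting level.

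If the printed count were used, three things could follow:

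- The child stays on 16 IU/day, so the dose optimization the step is meant to provide does not happen.
- The bottle-weight check gives a false signal, in either arm, whenever the count the family uses differs from the count behind the expected use. A child using 4 sprays looks non-compliant against an expectation of 6, and a child correctly using 6 looks like an over-user against an expectation of 4.
- A child on active drug recorded at 24 IU but taking 16 IU enters the weight-based dosing analysis with too high a dose.

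Week 2 is a remote visit (Study Time Commitment and Reduction of Burden). The documents do not say which of the two texts the clinician or the pharmacy works from.

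**Working it through.** **Inputs**

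- Strength: 4 IU per spray (Research Strategy And Feasibility).
- Dose and spray pairs: 16 IU as 4 sprays and 12 IU as 3 sprays (both places); 24 IU as 6 sprays (Research Strategy); 24 IU as 4 sprays (Titration Schedule).

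**Step 1: implied strength of each pair (daily dose / sprays per day)**

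| Pair | Source | IU per spray |
|---|---|---|
| 16 IU, 4 sprays | both | 16/4 = 4 |
| 12 IU, 3 sprays | both | 12/3 = 4 |
| 24 IU, 6 sprays | Research Strategy | 24/6 = 4 |
| 24 IU, 4 sprays | Titration Schedule | 24/4 = **6** |

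Only the last pair departs from 4 IU. No 6 IU spray is described anywhere. The adult autism study in Preliminary Study 1 gives 24 IU as 3 puffs in each nostril, which is 24/6 = 4 IU per puff and agrees with the first three pairs.

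**Step 2: dose delivered by the printed count**

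4 sprays x 4 IU = 16 IU/day, the starting dose. Shortfall: 24 - 16 = 8 IU/day, and 8/24 = 33%. The printed 24 IU is not reproduced.

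**Step 3: correct count**

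24 IU / 4 IU per spray = 6 sprays per day.

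**Step 4: effect on the bottle-weight check**

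Assumptions: escalation on day 14, full adherence, 56 treatment days, and different counts behind actual and expected use.

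- Weeks 2 to 8 (42 days): 42 x 4 = 168 sprays and 42 x 6 = 252 sprays. Taking 4 against an expected 6 shows 168/252 = 67%; taking 6 against an expected 4 shows 252/168 = 150%.
- All 8 weeks: the first 14 days add 14 x 4 = 56 sprays, giving 224 and 308. The ratios are 224/308 = 73% and 308/224 = 138%.
- By dispensing period: the Schedule of Events marks treatment given at baseline, week 4 and week 8, so weighing may follow those intervals. Weeks 0 to 4: 56 + 14 x 4 = 112 and 56 + 14 x 6 = 140, hence 112/140 = 80% or 140/112 = 125%. Weeks 4 to 8: 28 x 4 = 112 and 28 x 6 = 168, hence 67% or 150%.

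**Step 5: effect on the recorded dose**

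Recorded/taken = 24/16 = 1.5, an overstatement of 50%. Body weight cancels, so the ratio is the same for any child.

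**The case against.** The best defence is that this is a slip in one parenthesis and that the protocol already contains the right instruction. The Research Strategy paragraph is the only place that defines the spray strength, and it gives all three steps correctly. The error also reveals itself: the preceding paragraph of the Titration Schedule pairs 4 sprays with 16 IU, and the clinician, the PI and the parent would all have to accept an increase to the same number.

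The consequences are conditional as well. If family and pharmacy both use 4, or both use 6, the bottle weights show nothing odd. If they differ, the stated response is that the team takes it up with the family, which would tend to expose the error. The weeks 2 to 8 and whole-study percentages need not match how bottles are dispensed and weighed. The dosing analysis is exploratory, and the plan does not say whether dose is recorded in IU or in sprays. The main analysis is intent-to-treat regardless of compliance.

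All of this stands as a limit on the harm. None of it makes the printed count right or removes the conflict between two current texts on the same dosing step. The case for correction does not rest on the size of the percentages.

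**Conclusion.** The point holds. At 4 IU per spray, the Titration Schedule's 4 sprays for 24 IU/day is wrong, and the correct count is 6. The dose is not in doubt, because 24 IU appears consistently in the Objective, Background and Significance, Research Strategy and the Titration Schedule itself.

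Read literally, the rule leaves an escalated child 33% below the intended dose. Any distortion of the compliance check or the dosing analysis depends on the printed count being used, and for compliance on the two counts being mixed. How many children this could involve is unknown.

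The child would stay on the protocol's own starting dose, so there is no overexposure, and sample size, power and alpha are unaffected. The error must nevertheless be corrected, because it is a wrong figure in the operative dosing rule of a paediatric drug trial.

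**What to change.** In the lack-of-response paragraph of the Titration Schedule, change the spray count for 24 IU/day from 4 to 6 per day, matching Research Strategy And Feasibility. Then confirm that the clinician and pharmacy dosing instructions use 6 sprays per day from the date of escalation, and that the expected use in the bottle-weight check does the same.

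The cost is a one-digit correction and a check of those instructions. No extra patients, visits or procedures are needed.
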